## Output 4.2 Concomitant Medications by Medication Class and Preferred Name (CMT01A)

Protocol: GB41149

Analysis Population: Safety-evaluable population

ATC Class Level 2 Other Treatment	Placebo (N = XXX)	MTPS9579A Active (N = XXX)	All Patients (N=nnn)
Total number of patients with at least one treatment	nn (xx.x%)	nn (xx.x%)	nn (xx.x%)
Total number of treatments	nnn	nnn	nnn
AGENTS ACTING ON THE RENIN-ANGIOTENSIN SYSTEM			
Total number of patients with at least one treatment	nn (xx.x%)	nn (xx.x%)	nn (xx.x%)
Total number of treatments	nnn	nnn	nnn
RAMIPRIL	nn (xx.x%)	nn (xx.x%)	nn (xx.x%)
...			
Class 2			
Total number of patients with at least one treatment	nn (xx.x%)	nn (xx.x%)	nn (xx.x%)
Total number of treatments	nnn	nnn	nnn
Other treatment 1	nn (xx.x%)	nn (xx.x%)	nn (xx.x%)
...			

## Output 4.3 Concomitant Medications by Preferred Name (CMT02\_PT)

Protocol: GB41149

Analysis Population: Safety-evaluable population

Other Treatment	Placebo (N = XXX)	MTPS9579A Active (N = XXX)	All Patients (N=nnn)
Total number of patients with at least one treatment	nn (xx.x%)	nn (xx.x%)	nn (xx.x%)
Total number of treatments	nnn	nnn	nnn
Other treatment 1	nn (xx.x%)	nn (xx.x%)	nn (xx.x%)
Other treatment 2	nn (xx.x%)	nn (xx.x%)	nn (xx.x%)
...			

## Output 4.4 Overview of Deaths and Adverse Events (AET01)

Protocol: GB41149

Analysis Population:

- (1) Placebo Run-in Period; Run-in safety-evaluable population (PERIOD1\_PEFL)
- (2) 48-Week Double-Blind Treatment Period and 12-Week Safety Follow-up Period; Safety-evaluable population (PERIOD2\_SE)

	Placebo (N = XXX)	MTPS9579A Active (N = XXX)	All Patients (N = XXX)
Total number of patients with at least one AE	nn (xx.x%)	nn (xx.x%)	nn (xx.x%)
Total number of AEs	nn	nn	nn
Total number of deaths	nn (xx.x%)	nn (xx.x%)	nn (xx.x%)
Total number of patients withdrawn from study due to an AE	nn (xx.x%)	nn (xx.x%)	nn (xx.x%)

Total number of patients with at least one			
AE with fatal outcome	nn (xx.x%)	nn (xx.x%)	nn (xx.x%)
Serious AE	nn (xx.x%)	nn (xx.x%)	nn (xx.x%)
Serious AE leading to withdrawal from treatment	nn (xx.x%)	nn (xx.x%)	nn (xx.x%)
Serious AE leading to dose modification/interruption	nn (xx.x%)	nn (xx.x%)	nn (xx.x%)
Related Serious AE	nn (xx.x%)	nn (xx.x%)	nn (xx.x%)
AE leading to withdrawal from treatment	nn (xx.x%)	nn (xx.x%)	nn (xx.x%)
AE leading to dose modification/interruption	nn (xx.x%)	nn (xx.x%)	nn (xx.x%)
Related AE	nn (xx.x%)	nn (xx.x%)	nn (xx.x%)
Related AE leading to withdrawal from treatment	nn (xx.x%)	nn (xx.x%)	nn (xx.x%)
Related AE leading to dose modification/interruption	nn (xx.x%)	nn (xx.x%)	nn (xx.x%)
Grade 3-5 AE	nn (xx.x%)	nn (xx.x%)	nn (xx.x%)

## Output 4.5 Deaths (DTHT01)

Protocol: GB41149

Analysis Population: Safety-evaluable population

	Placebo (N=xx)	MTPS9579A Active (N=xx)	All patients (N=xxx)
Total number of deaths	nn	nn	nn

Primary cause of death	nn	nn	nn
N			
Adverse event	nn (xx.x%)	nn (xx.x%)	nn (xx.x%)
Progressive disease	nn (xx.x%)	nn (xx.x%)	nn (xx.x%)
Other	nn (xx.x%)	nn (xx.x%)	nn (xx.x%)

Percentages for Total Number of Deaths are relative to total N.

All other percentages are relative to n within each module.

## Output 4.6 Adverse Events Resulting in Death (AET07)

Protocol: GB41149

Analysis Population: Safety-evaluable population

MedDRA SOC and Preferred Term	Placebo (N = XXX)	MTPS9579A Active (N = XXX)	All Patients (N = XXX)
Total number of deaths	nn (xx.x%)	nn (xx.x%)	nn (xx.x%)
SOC1 / PT 1	nn (xx.x%)	nn (xx.x%)	nn (xx.x%)
SOC2 / PT 2	nn (xx.x%)	nn (xx.x%)	nn (xx.x%)
SOC3 / PT 3	nn (xx.x%)	nn (xx.x%)	nn (xx.x%)
SOC4 / PT 4	nn (xx.x%)	nn (xx.x%)	nn (xx.x%)
...			

## Output 4.7 Adverse Events (AET02)

Protocol: GB41149

Analysis Population:

- (1) Placebo Run-in Period; Run-in safety-evaluable population (PERIOD1\_PEFL)
- (2) 48-Week Double-Blind Treatment Period and 12-Week Safety Follow-up Period; Safety-evaluable population (PERIOD2\_SE)
- (3) 3 patients that were administered saline by IV infusion without IP at week18 visit (DEVI)
- (4) Grade 3+ adverse events (GRD3)

MedDRA System Organ Class MedDRA Preferred Term	Placebo (N = XXX)	MTPS9579A Active (N = XXX)	All Patients (N = XXX)
Total number of patients with at least one adverse event	nn (xx.x%)	nn (xx.x%)	nn (xx.x%)
Overall total number of events	nn	nn	nn
SOC 1			
Total number of patients with at least one adverse event	nn (xx.x%)	nn (xx.x%)	nn (xx.x%)
Total number of events	nn	nn	nn
PT 1	nn (xx.x%)	nn (xx.x%)	nn (xx.x%)
PT 2	nn (xx.x%)	nn (xx.x%)	nn (xx.x%)
PT 3	nn (xx.x%)	nn (xx.x%)	nn (xx.x%)
PT 4			
...			

## Output 4.8 Adverse Events Leading to Study Treatment Discontinuation (AET02)

Protocol: GB41149

Analysis Population: 48-Week Double-Blind Treatment Period and 12-Week Safety Follow-up Period; Safety-evaluable population (PERIOD2\_SE)

[Similar to output 4.7]

## **Output 4.9 Adverse Events Leading to Study Discontinuation (AET02)**

Protocol: GB41149

Analysis Population: 48-Week Double-Blind Treatment Period; Safety-evaluable population

[Similar to output 4.7]

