2.1 EFFICACY OBJECTIVES

2.1.1 Primary Efficacy Objective

The primary efficacy objective for this study is to evaluate the efficacy of MTPS9579A compared with placebo on the basis of the following endpoint:

- Time to first CompEx event (Fuhlbrigge et al. 2017), a composite endpoint defined as time from randomization to first asthma exacerbation or diary worsening during the 48-week double-blind treatment period (from the randomization visit [Week 2] to end of treatment [Week 50]). Asthma exacerbations and diary worsening are defined as follows:

Asthma exacerbations are assessed by the investigator and defined as new or increased asthma symptoms (wheezing, coughing, dyspnea, chest tightness, and/or nighttime awakenings due to these symptoms) that result in one or both of the following:

- Hospitalization or an emergency department or urgent care visit requiring administration of systemic corticosteroid treatment
- Treatment with systemic (IV, intramuscular [IM], or oral) corticosteroids for ≥ 3 days or a long-acting depot corticosteroid preparation with a therapeutic effectiveness of ≥ 3 days
- Diary worsening is based on the occurrence of prespecified changes (deteriorations) in a subset of the following six parameters: morning peak expiratory flow rate (PEFR), evening PEFR, morning symptom score, evening symptom score, morning short-acting rescue therapy use, and evening short-acting rescue therapy use. A detailed definition of diary worsening is provided in Section 6.4.1.

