3. STUDY DESIGN

3.1 OVERVIEW OF THE STUDY DESIGN

This is a Phase IIa, randomized, placebo-controlled, double-blind, multicenter, two-arm study of MTPS9579A compared with placebo as an add-on therapy in patients with uncontrolled moderate to severe asthma who are receiving daily ICS therapy and at least one of the following additional controller medications: LABA, leukotriene modulator (leukotriene modifier [LTM] or leukotriene receptor antagonist [LTRA]), long-acting muscarinic antagonist (LAMA), or long-acting theophylline preparation. The study *initially was to* randomize approximately 160 patients at approximately 55 sites globally. *However, as of March 2021, study enrollment was halted with 134 patients enrolled, and in August 2021, a decision was made to permanently halt further enrollment.*

This study will consist of a 12–28 day screening period, a 2-week single-blind placebo run-in period, a 48-week double-blind treatment period, a safety follow-up visit at Week 54, and a safety follow-up phone call at Week 58. During the screening period, patients must demonstrate acceptable inhaler, peak flow meter, and spirometry techniques, in addition to compliance with required, twice-daily use of an electronic diary (eDiary) for answering questions related to asthma symptoms, PEFR, and short-acting rescue therapy use (see Section 4.5.8). Patients who fail to meet eligibility criteria during the screening period will be permitted to re-screen once as described in Section 3.1.1.

Patients who meet enrollment criteria for the run-in period will receive one single-blind dose of placebo (Week 0) to allow for the evaluation of variability in asthma control. At the randomization visit (Week 2), patients must meet additional eligibility criteria for the double-blind treatment period that includes continued compliance with required, twice-daily use of the eDiary (see Section 4.1.1.2).

[figure not shown]
Patients will be randomized in a 1:1 ratio to receive MTPS9579A (1800 mg IV Q4W) or placebo as described in Section 4.2. Study drug will be administered by IV infusion at the randomization visit (Week 2), Week 6, and every 4 weeks thereafter through Week 46.

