## Output 4.35 Listing of Adverse Events Leading to Study Discontinuation (AEL02\_ED)

Protocol: GB41149

Analysis Population: 48-Week Double-Blind Treatment Period and 12-Week Safety Follow-up Period; Safety-evaluable population (PERIOD2\_SE)

[Similar to output 4.32]

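### SAP Output 4.9 tabulates adverse events leading to study discontinuation for the 48-week period only, while the overview row and the listing of the same events also cover the 12-week safety follow-up

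*SAP*

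**What the plan says.** Output 4.9 follows the layout of Output 4.7, so it shows adverse events leading to study discontinuation by system organ class and preferred term. Its population line reads "48-Week Double-Blind Treatment Period; Safety-evaluable population". It mentions no follow-up and carries no filter code.

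The outputs that sit closest to it use a longer window:

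- Output 4.35, titled "Listing of Adverse Events Leading to Study Discontinuation", lists the same events and is specified for "48-Week Double-Blind Treatment Period and 12-Week Safety Follow-up Period; Safety-evaluable population", with the filter PERIOD2_SE.
- Output 4.4, the overview, has a row "Total number of patients withdrawn from study due to an AE". Its post-randomization version uses the same longer window and filter.
- Output 4.8, the companion table for events leading to treatment discontinuation, comes immediately before 4.9, shares its template and also uses PERIOD2_SE.

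Protocol Section 6.5 asks for a separate summary of adverse events leading to discontinuation from the study. Of the SAP's tables, Output 4.9 is the one that gives it by term.

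On timing, Protocol Section 2.1.1 places the double-blind period between Week 2 and Week 50. Section 3.1 has dosing at Week 2, at Week 6 and "every 4 weeks thereafter through Week 46", followed by "a safety follow-up visit at Week 54, and a safety follow-up phone call at Week 58". Section 5.3.1 collects adverse events until 12 weeks after the final dose or until discontinuation from the study, whichever is later.

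**The concern.** One concept, withdrawal from the study because of an adverse event, is reported as an overview count, a by-term table and a listing. The count and the listing share one window, and the table between them has a shorter one. A reader who adds up the by-term table may not recover the overview count and would find no footnote to say why. The table at risk of being short is the one that groups by treatment arm the events that led patients to leave. Adverse events are still being collected during follow-up, so the data for the longer window will exist.

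**Working it through.** The plan states no figure to reproduce. The check compares the specified windows and then does simple date arithmetic.

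**Step 1. Windows side by side (post-randomization versions).**

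| SAP output | Content | Follow-up included? | Filter code |
|---|---|---|---|
| 4.4 | Overview, with a row for withdrawal from study due to an AE | Yes | PERIOD2_SE |
| 4.8 | AEs leading to treatment discontinuation, by term | Yes | PERIOD2_SE |
| **4.9** | **AEs leading to study discontinuation, by term** | **No** | **none** |
| 4.35 | Listing of AEs leading to study discontinuation | Yes | PERIOD2_SE |

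Outputs 4.7 and 4.10 to 4.16 each have a PERIOD2_SE version as well. Among the adverse event tables that state a post-randomization window, 4.9 is the only one that leaves out follow-up.

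**Step 2. Length of the gap for a patient dosed through Week 46.**

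- End of the longer window: Week 46 + 12 weeks = Week 58.
- End of the double-blind period: Week 50.
- Difference: 58 − 50 = 8 weeks. The Schedule of Activities agrees: Day 408 − Day 352 = 56 days = 8 weeks.

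For a patient who stops dosing early, the gap depends on how the SAP bounds the two periods for that patient, and it does not say.

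**Step 3. Which events fall in the gap.** The SAP does not state how an adverse event is assigned to a period. Assume first that onset decides, which is how Protocol Section 6.5 frames treatment-emergent events (new or worsening events).

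- Onset Week 48, withdrawal Week 52: in 4.4, 4.9 and 4.35. Nothing is lost.
- Onset Week 52, withdrawal before Week 58: in 4.4 and 4.35, absent from 4.9.

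If the date of withdrawal decided instead, the first example would also drop out of 4.9. Under either rule the outputs can disagree, but the onset rule gives the smaller loss.

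**Step 4. Size.** The documents contain no adverse event counts, so the number of affected patients cannot be computed. For scale, SAP Output 1.1 shows 65 placebo and 69 MTPS9579A patients in the safety-evaluable population. One omitted patient would change an arm's figure by 1/65 = 1.5% or 1/69 = 1.4%.

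**The case against.** The best counter-argument is that this is an incomplete label. Period-restricted outputs in the SAP usually carry a code: PERIOD2_SE for the period with follow-up, or PHASE2_SE for the double-blind period alone (Outputs 4.18, 4.27 and 4.28). Output 4.9 has neither, so a truncated header is as plausible as a deliberate restriction. That stands as an account of how it arose. It does not remove the problem, because the SAP is the programming specification and, as written, it asks for a different window.

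Second, the treatment-emergent definition in Protocol Section 6.5 refers to the 48-week double-blind period and does not mention follow-up. On one reading, 4.9 is the output that matches the Protocol. The sentence is ambiguous, since the reference to the 48-week period may qualify the first dose only. If the narrow reading governed, 4.4, 4.8 and 4.35 would be the ones out of line, so the outputs need reconciling either way.

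Third, the information is not lost. Listing 4.35 shows each event by preferred term, follow-up included, and 4.4 gives the total. This is correct, and it keeps the point minor.

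Fourth, few events can be affected. After Week 50 only one visit and one telephone call remain, and the last planned dose was at Week 46. This is also correct.

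**Conclusion.** The inconsistency is real and unexplained, and its consequence is small. Assuming assignment by onset and dosing through Week 46, Output 4.9 would miss only events that start in about Weeks 50 to 58 and lead to study withdrawal. There may be none.

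Three stronger readings are tempting, and the documents do not support them:

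- A reader might infer that every patient who leaves after Week 50 because of an adverse event is missing from 4.9. Under assignment by onset, a patient whose event began earlier is still included.
- A reader might set the 8 weeks against the 56 weeks from Week 2 to Week 58 and take the ratio as the share of withdrawals missed. It is a share of calendar time. The documents say nothing about how withdrawals are spread over that time.
- A reader might infer that 4.9 is the only safety table without follow-up. Output 4.18 is also limited to the double-blind period, and Outputs 4.5 and 4.6 state no period. The contrast holds only among adverse event tables with a stated window.

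**What to change.** In SAP Output 4.9, replace the population line with "48-Week Double-Blind Treatment Period and 12-Week Safety Follow-up Period; Safety-evaluable population" and add the code (PERIOD2_SE), so that the table reconciles with Outputs 4.4, 4.8 and 4.35. This is the smaller edit, because the other adverse event tables with a stated post-randomization window already include follow-up. If the shorter window was intended, keep it and add a footnote that gives the reason and says the table may not sum to the overview row. Either way the cost is one line of SAP text and a filter setting, with no new data or analysis method.

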## **Output 4.10 Serious Adverse Events (AET02)**

Protocol: GB41149

Analysis Population:

- (1) Placebo Run-in Period; Run-in safety-evaluable population (PERIOD1\_PEFL)
- (2) 48-Week Double-Blind Treatment Period and 12-Week Safety Follow-up Period; Safety-evaluable population (PERIOD2\_SE)

[Similar to output 4.7]

## **Output 4.11 Adverse Events Related to Study Treatment (AET09)**

Protocol: GB41149

Analysis Population:

- (1) Placebo Run-in Period; Run-in safety-evaluable population (PERIOD1\_PEFL)
- (2) 48-Week Double-Blind Treatment Period and 12-Week Safety Follow-up Period; Safety-evaluable population (PERIOD2\_SE)

[Similar to output 4.7]

## **Output 4.12 Serious Adverse Events Related to Study Treatment (AET02)**

Protocol: GB41149

Analysis Population:

- (1) Placebo Run-in Period; Run-in safety-evaluable population (PERIOD1\_PEFL)
- (2) 48-Week Double-Blind Treatment Period and 12-Week Safety Follow-up Period; Safety-evaluable population (PERIOD2\_SE)

[Similar to output 4.7]

## **Output 4.13 Adverse Events by Preferred Term (AET02)**

Protocol: GB41149

Analysis Population:

- (1) Placebo Run-in Period; Run-in safety-evaluable population (PERIOD1\_PEFL)
- (2) 48-Week Double-Blind Treatment Period and 12-Week Safety Follow-up Period; Safety-evaluable population (PERIOD2\_SE)

	Placebo (N = XXX)	MTPS9579A Active (N = XXX)	All Patients (N = XXX)
MedDRA Preferred Term			
Total number of patients with at least one adverse event	nn (xx.x%)	nn (xx.x%)	nn (xx.x%)
Overall total number of events	nn	nn	nn
PT 1	nn (xx.x%)	nn (xx.x%)	nn (xx.x%)
PT 2	nn (xx.x%)	nn (xx.x%)	nn (xx.x%)
PT 3	nn (xx.x%)	nn (xx.x%)	nn (xx.x%)
PT 4			
...			

## Output 4.14 Adverse Events by Highest WHO Toxicity Grade (AET04)

Protocol: GB41149

Analysis Population:

- (1) Placebo Run-in Period; Run-in safety-evaluable population (PERIOD1\_PEFL)
- (2) 48-Week Double-Blind Treatment Period and 12-Week Safety Follow-up Period; Safety-evaluable population (PERIOD2\_SE)

MedDRA System Organ Class MedDRA Preferred Term	Placebo (N = XXX)	MTPS9579A Active (N = XXX)	All Patients (N = XXX)
Grade	Grade 1-2	nn (xx.x%)	nn (xx.x%)
- Any adverse events -	- Any Grade -	nn (xx.x%)	nn (xx.x%)
		nn (xx.x%)	nn (xx.x%)

	1	nn (xx.x%)	nn (xx.x%)	nn (xx.x%)
	2	nn (xx.x%)	nn (xx.x%)	nn (xx.x%)
	Grade 3-4	nn (xx.x%)	nn (xx.x%)	nn (xx.x%)
	3	nn (xx.x%)	nn (xx.x%)	nn (xx.x%)
	4	nn (xx.x%)	nn (xx.x%)	nn (xx.x%)
	Grade 5	nn (xx.x%)	nn (xx.x%)	nn (xx.x%)
BLOOD AND LYMPHATIC SYSTEM DISORDERS				
- Overall -	- Any Grade -	nn (xx.x%)	nn (xx.x%)	nn (xx.x%)
	Grade 1-2	nn (xx.x%)	nn (xx.x%)	nn (xx.x%)
	1	nn (xx.x%)	nn (xx.x%)	nn (xx.x%)
	2	nn (xx.x%)	nn (xx.x%)	nn (xx.x%)
	Grade 3-4	nn (xx.x%)	nn (xx.x%)	nn (xx.x%)
	3	nn (xx.x%)	nn (xx.x%)	nn (xx.x%)
	4	nn (xx.x%)	nn (xx.x%)	nn (xx.x%)
	Grade 5	nn (xx.x%)	nn (xx.x%)	nn (xx.x%)
NEUTROPENIAS	- Any Grade -	nn (xx.x%)	nn (xx.x%)	nn (xx.x%)
	Grade 1-2	nn (xx.x%)	nn (xx.x%)	nn (xx.x%)

1	nn (xx.x%)	nn (xx.x%)	nn (xx.x%)
2	nn (xx.x%)	nn (xx.x%)	nn (xx.x%)
Grade 3-4	nn (xx.x%)	nn (xx.x%)	nn (xx.x%)
3	nn (xx.x%)	nn (xx.x%)	nn (xx.x%)
4	nn (xx.x%)	nn (xx.x%)	nn (xx.x%)
Grade 5	nn (xx.x%)	nn (xx.x%)	nn (xx.x%)

## Output 4.15 Adverse Event of Special Interest Summary Table (AET01\_AESI)

Protocol: GB41149

Analysis Population:

- (1) Placebo Run-in Period; Run-in safety-evaluable population (PERIOD1\_PEFL)
- (2) 48-Week Double-Blind Treatment Period and 12-Week Safety Follow-up Period; Safety-evaluable population (PERIOD2\_SE)

	Placebo (N = XXX)	MTPS9579A Active (N = XXX)	All Patients (N = XXX)
Total number of patients with at least one AE	nn (xx.x%)	nn (xx.x%)	nn (xx.x%)
Total number of AEs	nn	nn	nn
Total number of patients with at least one AE by worst grade			
Grade 1	nn (xx.x%)	nn (xx.x%)	nn (xx.x%)
Grade 2	nn (xx.x%)	nn (xx.x%)	nn (xx.x%)

Grade 3	nn (xx.x%)	nn (xx.x%)	nn (xx.x%)
Grade 4	nn (xx.x%)	nn (xx.x%)	nn (xx.x%)
Total number of patients with study drug withdrawn due to AE	nn (xx.x%)	nn (xx.x%)	nn (xx.x%)
Total number of patients with dose modified/interrupted due to AE	nn (xx.x%)	nn (xx.x%)	nn (xx.x%)
Total number of patients with treatment received for AE	nn (xx.x%)	nn (xx.x%)	nn (xx.x%)
Total number of patients with all non-fatal AEs resolved	nn (xx.x%)	nn (xx.x%)	nn (xx.x%)
Total number of patients with at least one unresolved or ongoing non-fatal AE	nn (xx.x%)	nn (xx.x%)	nn (xx.x%)
Total number of patients with at least one serious AE	nn (xx.x%)	nn (xx.x%)	nn (xx.x%)
Total number of patients with at least one related AE	nn (xx.x%)	nn (xx.x%)	nn (xx.x%)

## Output 4.16 Adverse Events by System Organ Class and Preferred Term (AET01\_ADA)

Protocol: GB41149

Analysis Population:

- (1) Placebo Run-in Period; Run-in safety-evaluable population (PERIOD1\_PEFL)
- (2) 48-Week Double-Blind Treatment Period and 12-Week Safety Follow-up Period; Safety-evaluable population (PERIOD2\_SE)

MedDRA System Organ Class MedDRA Preferred Term	ADA- (N = XXX)	ADA+ (N = XXX)
Total number of patients with at least one adverse event	nn (xx.x%)	nn (xx.x%)
Overall total number of events	nn	nn
SOC 1		
Total number of patients with at least one adverse event	nn (xx.x%)	nn (xx.x%)
Total number of events	nn	nn
PT 1	nn (xx.x%)	nn (xx.x%)
PT 2	nn (xx.x%)	nn (xx.x%)
PT 3	nn (xx.x%)	nn (xx.x%)
PT 4	nn (xx.x%)	nn (xx.x%)
...		

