- Time to first CompEx event (as defined in primary efficacy objective) within subgroups defined by blood eosinophils during the 48-week double-blind treatment period
- Rate of asthma exacerbations in subgroups defined by mutations in the genes encoding tryptase (*TPSAB1* and *TPSB2*) during the 48-week double-blind treatment period
- Time to first CompEx event (as defined in primary efficacy objective) in subgroups defined by mutations in the genes encoding tryptase (*TPSAB1* and *TPSB2*) during the 48-week double-blind treatment period

Study Design

Description of Study

This is a Phase IIa, randomized, placebo-controlled, double-blind, multicenter, two-arm study of MTPS9579A compared with placebo as an add-on therapy in patients with uncontrolled moderate to severe asthma who are receiving daily ICS therapy and at least one of the following additional controller medications: long-acting β -agonist (LABA), leukotriene modulator (leukotriene modifier [LTM] or leukotriene receptor antagonist [LTRA]), long-acting muscarinic antagonist (LAMA), or long-acting theophylline preparation. The study *initially was to* randomize approximately 160 patients at approximately 55 sites globally. *However, as of March 2021, study enrollment was halted with 134 patients enrolled, and in August 2021, a decision was made to permanently halt further enrollment.*

This study will consist of a 12–28 day screening period, a 2-week single-blind placebo run-in period, a 48-week double-blind treatment period, a safety follow-up visit at Week 54, and a safety follow-up phone call at Week 58. During the screening period, patients must demonstrate acceptable inhaler, peak flow meter, and spirometry techniques, in addition to compliance with required, twice-daily use of an electronic diary (eDiary) for answering questions related to asthma symptoms, PEFR, and short-acting rescue therapy use. Patients who fail to meet eligibility criteria during the screening period will be permitted to re-screen once as described in the protocol.

Patients who meet enrollment criteria for the run-in period will receive one single-blind dose of placebo (Week 0) to allow for the evaluation of variability in asthma control. At the randomization visit (Week 2), patients must meet additional eligibility criteria for the double-blind treatment period that includes continued compliance with required, twice-daily use of the eDiary.

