6.7 IMMUNOGENICITY ANALYSES

The immunogenicity analysis population will consist of all patients with at least one ADA assessment. Patients will be grouped according to treatment received or, if no treatment is received prior to study discontinuation, according to treatment assigned.

The numbers and proportions of ADA-positive patients and ADA-negative patients at randomization (baseline prevalence) and after drug administration (postbaseline incidence) will be summarized by treatment group. When determining postbaseline incidence, patients are considered to be ADA positive if they are ADA negative or have missing data at baseline but develop an ADA response following study drug exposure (treatment-induced ADA response), or if they are ADA positive at baseline and the titer of one or more postbaseline samples is at least 0.60 titer unit greater than the titer of the baseline sample (treatment-enhanced ADA response). Patients are considered to be ADA negative if they are ADA negative or have missing data at baseline and all postbaseline samples are negative, or if they are ADA positive at baseline but do not have any postbaseline samples with a titer that is at least 0.60 titer unit greater than the titer of the baseline sample (treatment unaffected).

The relationship between ADA status and safety, efficacy, PK, and biomarker endpoints will be analyzed and reported via descriptive statistics.

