Appendix 1: Schedule of Activities

- ^m Vital signs and a focused physical examination (e.g., for signs of hypersensitivity reaction) will be monitored serially (every 15 [\pm 3] minutes) during both study drug administration and for the first hour immediately after dosing. Thereafter, vital signs and a focused physical examination will be performed every hour (\pm 10 minutes) ending at the investigator's discretion.
- ⁿ Concomitant therapy consists of any medication (e.g., prescription drugs, over-the-counter drugs, vaccines, herbal or homeopathic remedies, nutritional supplements) used by a patient in addition to protocol-mandated treatment from 7 days prior to screening (for medications not intended for the treatment of asthma) or 3 months prior to screening (for medications intended for the treatment of asthma) to the study completion/discontinuation visit.
- ^o Urine drug screen includes, but is not limited to, amphetamines, barbiturates, benzodiazepines, cocaine, cotinine, marijuana/cannabinoids (tetrahydrocannabinol), methadone, methamphetamines, methylenedioxymethamphetamine, opiates, and phencyclidine.
- ^p Hematology includes WBC count, RBC count, hemoglobin, hematocrit, platelet count, and differential count (neutrophils, eosinophils, basophils, monocytes, lymphocytes, other cells).
- ^q Only to be performed after the patient is randomized.
- ^r Chemistry panel (serum or plasma) includes sodium, potassium, chloride, bicarbonate or total carbon dioxide (if considered standard of care for the region), glucose, BUN or urea, creatinine, calcium, magnesium, phosphate, total protein, albumin, total and direct bilirubin, ALP, ALT, AST, urate, LDH, creatinine kinase, and hemoglobin A1c.
- ^s Urinalysis includes dipstick (pH, specific gravity, glucose, protein, ketones, bilirubin, nitrite, blood) and microscopic examination (sediment, RBCs, WBCs, casts, crystals, epithelial cells, bacteria). If urinalysis is abnormal, reflex testing for culture and antibiotic sensitivity should be performed if clinically indicated.
- ^t All women of childbearing potential will have a serum pregnancy test at screening. Urine pregnancy tests will be performed at specified subsequent visits. If a urine pregnancy test is positive, dosing should be held and a serum pregnancy test performed for confirmation.

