Appendix 1: Schedule of Activities

- ^y Prohibited medication use prior to spirometry is described in Section 4.4.4. If the patient has used a bronchodilator within the time window defined in Section 4.4.4, then the visit must be rescheduled. To accommodate the rescheduled visit, the usual visit window during the treatment period may be extended to \pm 4 days for Week 2, \pm 5 days for Week 3, and \pm 6 days for all other visits.
- ^z Patients will use an eDiary to record asthma symptoms, PEFR, and use of short-acting rescue therapy twice daily prior to taking asthma controller medications. Refer to Section 4.5.8 for compliance requirements. The eDiary will remind patients twice daily to complete their entries and will provide a time window during which the entry must be completed at approximately the same time each day. On the days of study visits, if the patient has not performed the morning PEFR measurement before arrival at the clinic, the PEFR should be measured at the clinic (see Section 4.5.8.2).
- ^{aa} On all study drug administration days that require PK serum sampling, PK samples will be obtained pre-dose and post-dose (2 hours \pm 30 minutes *after the end of the dose*). On clinic visit days where study drug is not administered and PK serum sampling is required, only one PK sample is to be obtained.
- ^{bb} To be collected predose.
- ^{cc} Samples will also be used for PK and biomarker analyses.
- ^{dd} Not applicable for a site that has not been granted approval for WGS.
- ^{ee} After informed consent has been obtained but prior to initiation of study drug, only serious adverse events caused by a protocol-mandated intervention should be reported. After initiation of study drug, all adverse events will be reported until 84 days after the final dose of study drug or end of study (Week 58) for patients who discontinue study drug but remain on study, whichever occurs later, or 6 weeks following the placebo dose for patients who failed to be randomized. After this period, the Sponsor should be notified if the investigator becomes aware of any serious adverse event that is believed to be related to prior study drug treatment (see Section 5.6).
- ^{ff} Patients should be administered the study drug over 1 hour, and observed for 1 hour post-infusion, with observation ending at the investigator's discretion (as described in footnote "m").

Appendix 2
Asthma Control Questionnaire, 5-Item Version

**ASTHMA CONTROL
QUESTIONNAIRE (ACQ)**

© 1997

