**Programming notes:**

ADA Evaluable Patients are defined as patients with non-missing ADA status (Either Positive or Negative), ADA status is in the ADAB dataset provided by the MSA team.

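### Output 4.16 splits placebo run-in events by an ADA status not yet measured, and its treatment-period version counts events before the first positive sample as ADA+ with no timing rule or person-time

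*SAP*

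**What the plan says.** Output 4.16 has two columns, ADA- and ADA+, and lists two analysis sets. Set (1) is the "Placebo Run-in Period; Run-in safety-evaluable population" (PERIOD1_PEFL). Set (2) is the "48-Week Double-Blind Treatment Period and 12-Week Safety Follow-up Period; Safety-evaluable population" (PERIOD2_SE). There is no treatment-arm column, no split by time of onset and no person-time row. The only programming note reads "ADA Evaluable Patients are defined as patients with non-missing ADA status (Either Positive or Negative", with the status taken from the ADAB dataset. It does not say whether that status is baseline, post-baseline or ever-positive.

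The protocol supplies the rest:

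- In the run-in, patients "will receive one single-blind dose of placebo (Week 0"; none receives MTPS9579A.
- In Appendix 1 the first ADA sample is at the randomization visit (Week 2), with the footnotes "Only to be performed after the patient is randomized" and "To be collected predose".
- Section 6.7 calls patients ADA-positive by one of two routes. Those negative or missing at baseline must "develop an ADA response following study drug exposure (treatment-induced ADA response". The others qualify "if they are ADA positive at baseline and the titer of one or more postbaseline samples is at least 0.60 titer unit greater" than the baseline titer (treatment-enhanced).
- Section 6.5 puts all run-in events in one group, because everyone had received placebo.
- Section 4.2 tests the randomization-visit ADA sample in all patients, but tests later placebo-arm samples only on request.

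**The concern.** The relationship between ADA status and safety is a stated exploratory endpoint (Protocol 2.4). Section 5.1.1.1 lists adverse events, along with reduced efficacy, as possible consequences of ADAs. Output 4.16 is the only SAP output split by ADA status, so it carries that question alone.

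The run-in version compares groups defined by something not yet measured and, for treatment-induced patients, not yet in existence. Any difference it shows is chance or patient mix.

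The treatment-period version labels a patient once and applies the label to the whole record. For treatment-induced patients, time before the first positive sample is counted as ADA+ time. This dilutes a true effect if there is one. Without person-time there is also a pull the other way: a patient who stays longer gives more samples, so has more chances to test positive, and also has more time to report events. At most 69 patients received MTPS9579A (Output 1.1), so the ADA+ column may be small and a few misplaced events could change its appearance.

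**Working it through.** **Population counts.** The SAP gives no figure for Output 4.16 itself. The counts in Output 1.1 reproduce: 66 + 69 = 135 randomized; 65 + 69 = 134 safety-evaluable; 65/66 = 98.5%; 134/135 = 99.3%.

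**Version (1), timing.** The run-in spans Week 0 to Week 2. MTPS9579A and ADA sampling both start at Week 2, with the sample taken before the dose. Every run-in event therefore precedes the first dose of MTPS9579A and the first ADA measurement. In addition, 140 - 135 = 5 of the 140 run-in patients (3.6%) were not randomized. They have no scheduled ADA sample, so they would fall out of both columns.

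**Version (2), share of events before the first positive sample.** Inputs from the protocol: first double-blind dose at Week 2; last dose at Week 46; 84 days of follow-up, so 46 + 84/7 = Week 58. Assumptions: constant adverse event rate, full follow-up to Week 58, and first positivity at Week *w*. The documents give no onset times, so *w* is varied over scheduled sampling weeks.

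Share before first positive = (*w* - 2)/(58 - 2)

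| First positive at Week | Calculation | Share of the patient's events |
|---|---|---|
| 6 | 4/56 | 7% |
| 14 | 12/56 | 21% |
| 22 | 20/56 | 36% |
| 30 | 28/56 | 50% |
| 38 | 36/56 | 64% |

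This applies to treatment-induced patients only. A treatment-enhanced patient already had ADAs at baseline.

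**Version (2), follow-up length.** The check was a simulation with no link between ADAs and events. It used ADA samples 4, 12, 20, 28, 36, 44 and 52 weeks after first dose, ADA incidence of 10-40%, study withdrawal of 10-30%, and only patients with at least one post-dose sample. ADA+ patients had 3-16% more events each than ADA- patients when ADA onset was spread evenly over time, and 2-8% more when onset was early (assumed mean 12 weeks). The excess was smallest at low withdrawal. Incidence, onset and withdrawal are all assumptions.

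**The case against.** The best defence is that version (2) follows the protocol. Section 6.7 classifies patients, not events, and promises only descriptive statistics, in a study that calls itself hypothesis-generating. The ADAB dataset is not shown, so silence on timing does not prove that dates are unavailable or would be ignored. The run-in line also appears in Outputs 4.4, 4.7 and 4.10 to 4.15, which suggests template carry-over. Patient-level columns are indeed the protocol's choice and should stay. What the defence does not supply is a reason for the run-in version, or any way to see in version (2) which events came before the first positive sample.

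A reader might also infer more than the documents support:

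- *Run-in events contaminate the treatment-period ADA+ column.* They do not; the two sets are separate tables.
- *All run-in events precede any ADA.* This is certain only for treatment-induced patients. Patients positive at baseline may already have had ADAs in the run-in, though none was measured then.
- *Adverse events are the main risk of ADAs.* Section 5.1.1.1 names them with reduced efficacy and ranks neither.
- *Events in the first four weeks of dosing always precede a positive result.* Week 6 is the first scheduled post-dose sample, but Appendix 6 asks for immunogenicity samples at a suspected anaphylactic reaction, so an earlier one is possible.
- *About half of ADA+ events are misplaced.* That figure follows from assuming evenly spread onset; other onset weeks give much smaller or larger shares.
- *Events before the first positive sample belong under ADA-.* Scheduled samples are mostly 8 weeks apart, so such a rule would move some true post-onset events into the wrong column.

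**Conclusion.** The point holds in two parts of different strength. Version (1) is wrong as written: it contradicts Protocol 6.5 and cannot inform the ADA-safety question. This rests on the text alone.

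Version (2) lacks a timing rule and person-time. For treatment-induced patients, about 7% to 64% of events would count as ADA+ before any positive sample, over first positivity from Week 6 to Week 38, with a constant event rate and follow-up to Week 58. This part rests on what the programming note omits. The follow-up-length effect is real but modest, and Protocol 4.6.1 limits it by keeping patients who stop treatment in follow-up to Week 58.

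The columns also need a defined population. As written, a placebo patient tested only at randomization could enter them on that single result. The defect is confined to the ADA-safety table and does not affect the efficacy outputs or the by-arm safety tables.

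**What to change.** 1. Delete the PERIOD1_PEFL set from Output 4.16. Run-in events remain in the other run-in safety tables.
2. In version (2), restrict the columns to MTPS9579A-treated patients, because post-randomization placebo samples are not routinely analysed.
3. Keep patient-level ADA+ and ADA- columns, and state that they use the Section 6.7 post-baseline classification.
4. Within ADA+, show treatment-induced patients' events separately by onset: before, and on or after, the date of the first qualifying positive sample. Give events per patient-year for each part and for the ADA- column.

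The cost is SAP wording, one merge of sample dates and a little more programming; no new data are collected. The downside is interpretive and needs a footnote. The first positive sample can lag true ADA onset by up to the sampling interval, mostly 8 weeks, so events in the before part are not proven to be pre-ADA.
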